Statistical Analyses:	
Analysis Sets:
 
Randomized Analysis Set will include all subjects who are randomized.
 
Safety Analysis Set will include all subjects in the Randomized Analysis Set who received at least one dose of study drug actually taken.
 
Modified intent-to-treat (mITT) Analysis Set will include all subjects in the Randomized Analysis Set who received at least one dose of randomized study drug.
 
Per-protocol (PP) Set will include all subjects in the mITT Analysis Set who are sufficiently compliant with the protocol. Criteria of sufficiently compliant will be detailed in SAP.
 
PK Analysis Set will include all subjects in the Safety Analysis Set who had at least one PK sample with measurable concentration.
 
PD Analysis Set will include all subjects in the Safety Analysis Set who had at least one measurable PD sample.
 
Efficacy Analyses:
 
Primary Efficacy Analyses:
 
The primary efficacy endpoint is a composite endpoint, including symptomatic recurrent venous thromboembolic disease, death as result of VTE, and no change or extension of thrombotic burden based on imaging during the first 3-month treatment period (ie, primary efficacy events occurring from randomization through the end of the 3-month treatment period). For subjects in Cohort 5, (ie, <6 months old), the primary efficacy endpoint is a composite endpoint consisting of the incidence of symptomatic recurrent VTE, death as a result of

VTE, and no change or extension of thrombotic burden within 6 to 12 weeks + 3 days. The primary efficacy analysis will be based on mITT Analysis Set. Analyses will be based on the randomized treatment even if a subject inadvertently receives the incorrect study drug.

In this analysis, the time to the first event of the composite primary efficacy outcome will be analyzed using a Cox's proportional hazard regression model including treatment and age groups as covariates.

The edoxaban-to-comparator hazard ratio will be computed with 95% confidence interval [CI] (two-sided) based on this model.

Edoxaban will be considered non-inferior to comparator if the upper limit of the 95% CI is <1.5.

If non-inferiority of edoxaban is established, edoxaban will be tested for superiority to comparator. Edoxaban will be considered superior to comparator if the upper limit of the 95 % CI from above analysis is <1.0.

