3.2. Discussion of Study Design

This study is designed to evaluate the PK and PD of edoxaban and to compare the efficacy and safety of edoxaban with SOC in pediatric subjects with confirmed VTE.

The adjudication of the efficacy and safety endpoints will be conducted by a blinded adjudication committee.

The study includes two periods:

- The Main Treatment Period is defined as the time from randomization, until the end of Month 3 of treatment. The Main Treatment Period for subjects <6 months old (Cohort 5) is defined as the time from randomization until the end of anticoagulant therapy for at least 6 to 12 weeks.
 - Subjects who early discontinue the Main Treatment Period will be monthly followed according to the Schedule of Events (Table 17.1) through Month 3 visit (Visit 5), or earlier (unscheduled interim visit at 6 weeks) for subjects in Cohort 5, and 30-day Follow-Up Visit (Visit 9).

- Subjects who complete the Main Treatment Period but do not continue into the Extension Period will be followed for 30 days after last dose of study drug (Visit 9).
- The Extension Period is discretionary for the Investigator and will include treatment from the end of the Main Treatment Period (Month 3, Visit 5) up through the end of Month 12 (Visit 8).
 - Subjects who discontinue the treatment at any time after Month 3 will have a Month 12/Discontinuation Visit (Visit 8) performed with the subsequent 30 day follow-up (Visit 9).
 - Subjects who complete Extension Period treatment at Month 12 (Visit 8) will be followed for 30 days after last dose of study drug (Visit 9).
- Subjects who require anticoagulant treatment after discontinuation of the study treatment at any time will be transitioned to a therapy as determined by the Investigator.

The study will attempt to recruit at least 10% of the subjects diagnosed with pulmonary embolism.

About 274 subjects will be included in this randomized study (137 subjects in each treatment arm) which will be conducted at clinical sites located worldwide.

Randomization will be stratified by age cohorts and by region (US/Canada, Europe, Asia/Pacific, and Rest of the World). The total duration of the study is expected to be approximately 4.5 years.

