5. STUDY TREATMENT(S)

5.1. Assigning Subjects to Treatments and Blinding

5.1.1. Treatment Group(s)

All subjects will be assessed for eligibility in the study in accordance with the inclusion/exclusion criteria after VTE diagnosis. Eligible subjects will be stratified by age and region (ie, US/Canada, Europe, Asia/Pacific, and Rest of the World), and then randomized in a 1:1 ratio to the edoxaban treatment arm or the SOC treatment arm, respectively.

Study treatment should be administered on the same day as randomization (Day 1). Subjects randomized to edoxaban and previously treated with VKA, can initiate edoxaban treatment only after the INR is ≤ 2.5 ; or 12 hours after last dose of LMWH.

The Day 5 PK/PD assessment will be adjusted accordingly to have 5 doses of edoxaban prior to assessment. For subjects participating in PK/PD assessment and receiving LMWH twice a day and who already received a morning dose on Day 1 prior to randomization, edoxaban can be started on the morning of Day 2 (12 hours \pm 3 hours after last evening dose of LMWH).

Initial treatment with heparin (with overlapping VKAs if needed) for index VTE prior to randomization must be within the range of at least 5 - 15 days and up to 20 days with Sponsor approval. In addition, prior to being randomized to edoxaban or SOC, subjects initially treated with VKA should have an INR ≤ 2.5 .

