5.1.2. Method of Treatment Allocation

Eligible subjects will be stratified by

1. Age (12 to <18 years of age; 6 to <12 years of age; 2 to <6 years of age; 6 months of age to <2 years of age; birth to <6 months of age)
2. Regions (ie US/Canada, Europe, Asia/Pacific and Rest of the World). Additional regions may be included if needed)

An independent biostatistician will generate the randomization schedule in accordance with the operating procedure for allocating study drug.

At randomization, the Investigator provides the IXRS with the study center number; the subject's presenting diagnosis (symptomatic VTE) and date of birth. Dose reduction stratification will take into account for:

- eGFR is 30-50% of normal for age and size (Appendix 17.7).
- Whether the subject is receiving concomitant treatment with P-gp inhibitors (Appendix 17.4.6).
- For all subject: whether body weight $<5^{\text{th}}$ percentile of subject's age (see Appendix 17.9).

The IXRS will assign the unique subject identification number, allocate the treatment group assignment for the subject and provide the appropriate drug supply kit number(s), for edoxaban and centrally sourced SOC.

A fax or e-mail will be sent by the IXRS to provide the appropriate drug supply kit number(s). The fax or e-mail will also provide a calendar with dates of subsequent prescheduled visits and drug resupply.

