11.4.1. Efficacy Analyses

11.4.1.1. Primary Efficacy Analyses

The primary efficacy analysis will be based on mITT Analysis Set. Analyses will be based on the randomized treatment arm even if a subject inadvertently receives the incorrect study drug. The primary efficacy endpoint is an event driven and a composite endpoint including symptomatic recurrent venous thromboembolic disease, death as result of VTE, and no change or extension of thrombotic burden from randomization to up to 3 months + 3 days from randomization. In this analysis, the time to the first event of the composite primary efficacy outcome will be analyzed using a Cox's proportional hazard regression model including treatment arm and age groups as covariates. Although this study is also stratified by region, region is not included in the model as a covariate because some age groups within regions may be very small due to the small overall sample size. The time to first event is defined as the time (days) from the day of randomization to the first event experienced by a subject during the 3 months + 3 days period. Subjects who did not have a primary efficacy outcome during the 3 months + 3 days period will be censored at 3 months + 3 days or the last day the subject had a complete assessment for study outcomes, whichever comes first. The edoxaban-to-comparator hazard ratio will be computed with 95% confidence interval (CI) (two-sided) based on this model. Edoxaban will be considered non-inferior to comparator if the upper limit of the 95% CI is ≤ 1.5 .

If non-inferiority of edoxaban is established, edoxaban will be tested for superiority to comparator. Edoxaban will be considered superior to comparator if the upper limit of the 95% CI from above analysis is ≤ 1.0 .

To control study-wise type I error, the testing for non-inferiority and superiority will follow the plan as described below.

The same proportional hazard model used for primary efficacy analysis will be performed for PP Analysis Set and Randomized Analysis Set as sensitivity analyses.

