11.4.1.2. Secondary Efficacy Analyses

The following secondary efficacy analyses will be conducted:

- A composite endpoint, including symptomatic recurrent venous thromboembolic disease, death as result of VTE, and no change or extension of thrombotic burden from the randomization to the date of the last dose of study drug + 30 days, the same Cox proportional hazards regression model used for the primary efficacy analysis will be used. The time to first event is defined as the time (days) from the day of randomization to the first event experienced by a subject from the randomization to the date of the last dose of study drug + 30 days. Subjects who did not have a primary efficacy outcome during the study period will be censored at the last day the subject had a complete assessment for study outcomes or the last study drug + 30 days, whichever came first. These efficacy analyses will be based on mITT and PP Analysis Sets. The incidence of this composite endpoint will also be summarized by treatment arm for the mITT and PP Analysis Sets.
- Incidence of all-cause mortality from randomization to the date of the last dose of study drug + 30 days will also be summarized by treatment arm for the mITT Analysis Set.
- The incidence of each component (symptomatic recurrent venous thromboembolic disease, death as result of VTE, and no change or extension of thrombotic burden) of the composite primary endpoint occurred during the first 3 month treatment period will be summarized by treatment arm for the mITT and PP Analysis Sets.

- The occurrence of DVT, catheter-related thrombosis, sinovenous thrombosis, and PE during the first 3-month treatment period, after the 3 month treatment period will be summarized by treatment arm for the mITT Analysis Set

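### Does leaving region, a randomisation stratum, out of every Cox model weaken the non-inferiority analysis?

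*Combined protocol and SAP*

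**What the plan says.** Section 3.2 sets the strata: "Randomization will be stratified by age cohorts and by region". Section 5.1.1 repeats this ("Eligible subjects will be stratified by age and region"), and Section 5.1.2 lets the list grow: "Additional regions may be included if needed".

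The Synopsis (Statistical Analyses) describes the primary analysis as a "proportional hazard regression model including treatment and age groups as covariates". Section 11.4.1.1 gives the same model, acknowledges that region is also a stratum, and explains its absence: "region is not included in the model as a covariate because some age groups within regions may be very small". The sentence goes on to give the underlying cause: these groups "may be very small due to the small overall sample size".

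No other model brings region back. For sensitivity, Section 11.4.1.1 states: "The same proportional hazard model used for primary efficacy analysis will be performed for PP Analysis Set and Randomized Analysis Set as sensitivity analyses". For the secondary composite, Section 11.4.1.2 states that "the same Cox proportional hazards regression model used for the primary efficacy analysis will be used". Sections 11.4.1.4 (net clinical outcome) and 11.4.3.1 (bleeding) also reuse it. Section 11.7 leaves detailed methods to a SAP finalised before database lock, and that text is not part of what was reviewed.

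**The concern.** An analysis is normally expected to reflect the factors used to stratify randomisation. Here one of the two is dropped, and no analysis in the available text uses it.

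The reason given also seems to miss its target. Small age groups within regions argue against a Cox model stratified on all crossed cells, or against an age-by-region interaction. An additive region term uses only the regional totals.

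There is a point specific to non-inferiority as well. Omitting a balanced prognostic factor from a Cox model pulls the hazard ratio towards 1. Under a null of no difference that is harmless or conservative. Under a non-inferiority null of 1.5 it pulls in the favourable direction. If the effect were sizeable, edoxaban could be declared non-inferior too easily.

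**Working it through.** **1. The plan's own figures (Section 11.6).** Margin 1.5, assumed hazard ratio 0.76, two-sided alpha 0.05, power 80%:

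events = 4 × (1.960 + 0.842)² / [ln(1.5/0.76)]² = 67.9, so 68.

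Subjects: with control risk 28% and the 24% reduction read as a risk ratio, the other arm has 0.76 × 28% = 21.3%, and 68/0.2464 = 276. Read as a hazard ratio, it has 1 − 0.72^0.76 = 22.1%, and 68/0.2505 = 272. The stated 274 lies between them. The design reproduces.

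**2. What the stated reason covers.**

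- Crossed cells: 5 × 4 = 20, averaging 13.7 subjects and 3.4 events. The sparsity is real.
- Regional totals: on average 274/4 = 68.5 subjects and 68/4 = 17 events.
- Parameters: treatment plus 4 age terms = 5, so 68/5 = 13.6 events per parameter. Adding 3 region terms gives 8, so 68/8 = 8.5.

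An additive term could be fitted, so the cell argument alone does not exclude it. The small overall size does support a small primary model.

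**3. Effect on the decision.** The documents give no event rates or subject shares by region, so these are assumptions. All simulations use 274 subjects and a control risk of 28% as the baseline.

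- A: 10,000 trials per setting; region shares 30/40/20/10%; age shares 40/20/15/15/10% with no age effect; blocks of 4; 64% of the cumulative hazard placed at the Month 3 image (18/28, from Sections 7.5 and 11.6); any region with fewer than 5 events merged into the largest when region is fitted.
- B: 2,000 trials; the same region shares and block size; assumed age effects; exponential times.
- C: 1,500 trials; exponential times.

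| Simulation | Assumed region effect | Non-inferior at HR 0.76, age only / with region (%) | Non-inferior at HR 1.5, age only / with region (%) |
|---|---|---|---|
| A | none | 78.1 / 78.0 | 2.9 / 3.0 |
| A | 2-fold spread | 78.4 / 78.5 | 3.3 / 3.5 |
| A | 4-fold spread | 78.7 / 78.4 | 3.4 / 3.4 |
| B | none | 77.5 / 77.7 | 3.2 / 3.2 |
| B | log-hazard SD 0.3 | 76.4 / 76.4 | 1.7 / 1.7 |
| B | log-hazard SD 0.6 | 75.7 / 76.1 | 2.6 / 2.2 |
| C | none | 79.9 / 80.1 | 2.5 / 2.5 |
| C | 2-fold spread | 80.4 / 80.6 | 2.2 / 2.3 |
| C | 4-fold spread | 79.6 / 80.3 | 2.9 / 2.5 |

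The largest difference between models is 0.7 points of power (C, 4-fold) and 0.4 points of false non-inferiority (B and C, strongest effect). The rates of 2.9 to 3.5% in A exceed the nominal 2.5%, but they do so under both models, so omitting region does not explain them.

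**4. Effect on the estimate.** With 68 events the standard error of the log hazard ratio is about 2/√68 = 0.243. In A it was 0.247 for age only and 0.248 with region. The large-sample Cox limit with region left out, under a 4-fold spread, is:

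- 0.766 for a within-region 0.760: ln(0.766/0.760) = 0.0079, and 0.0079/0.247 = 0.03 standard errors.
- 1.475 for a within-region 1.500: ln(1.500/1.475) = 0.0168, and 0.0168/0.243 = 0.07 standard errors.

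Under a 2-fold spread the limits are 0.7615 and 1.494. This is non-collapsibility: the age-only model estimates a region-averaged hazard ratio, which is a legitimate quantity and not a biased one.

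**5. Would a region-adjusted check be informative?** In A the two models gave different non-inferiority verdicts at HR 0.76 in 1.5, 2.7 and 4.5% of trials (none, 2-fold, 4-fold), about equally in each direction. The 1.5% arises with no region effect at all, so part of any disagreement is noise.

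**The case for a change.** The best case for acting concerns pre-specification, not bias. The comparator follows each site's own standard of care, so region could be prognostic. The trial is open-label. If a region-adjusted result were requested later, the handling of small or added regions would be decided with data in hand. One sentence now would settle it, and the 68 events and the primary test would not change. The plan also keeps age as a main effect although Cohort 5 may be small, so it does not treat sparse totals as disqualifying elsewhere. Nor can the missing SAP text be assumed to fill the gap: Section 11.4.1.3 lists no exploratory efficacy analyses, and the deferral in Section 11.4.3.6 sits under safety.

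Part of this stands. The rationale is loosely worded, an additive region term is feasible, and no region-adjusted analysis appears in the available text. It does not amount to a defect. The conclusion would still rest on the age-only model whatever the extra model showed, so the addition would be descriptive. The plan's caution about sparsity also has some substance. With an assumed region of 3% of subjects (about 2 of 68 events), the unmerged additive model failed to converge in 13.4% of simulated trials. That is mostly a nuisance: in a test fit with an event-free region, only that region's coefficient diverged, and the treatment estimate and its standard error were unchanged.

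**Conclusion.** The concern does not hold. The plan states that region is a stratum, states that it is left out, and gives a reason that is partly sound: a small trial supports a small model. The omission contradicts nothing in the plan and is fixed in advance. Compared with a model that adds region, the probability of concluding non-inferiority changes by at most 0.7 points under the design assumption and by at most 0.4 points at the margin. The hazard ratio shifts by about 0.03 of a standard error at 0.76 and 0.07 at 1.5, even with a four-fold spread in regional hazard. A sponsor could add a region-adjusted sensitivity model, but that is a preference and would alter no planned result or decision.

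These sizes rest on assumed region shares, region effects and block size, none of which the documents give. The 18% used in A to place events at the Month 3 image is the highest of the figures in Section 7.5, and according to Section 1.1 comes from 22 infants followed for 5 days to 4.2 years. B and C do not use it and lead to the same conclusion.

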- For subjects in whom clinicians prescribe warfarin, this will be started on Day 1. Heparin (exoxaparin or fondaparinux or UFH depending on the therapy received during pre-randomization period) will be discontinued when INR ≥ 2.0 and ≤ 3.0 for 2 consecutive measurements obtained at least 24 to 48 hours apart. The subject will continue warfarin for the remainder of the study treatment period.

The Investigator will use discretion to decide when and how often to repeat INR or anti-FXa levels or aPTT measurements or fondaparinux levels. These measurements will be taken in the clinic, or alternatively, optional site-specific local laboratory (Appendix 17.2).

6.3.3. Monthly Visits (Months 1 and 2; Visits 3 and 4) for both arms:

Starting with the Month 1 visit, subjects will return to the clinic every 30 days \pm 5 days (depending on the visit, see Schedule of Events in Appendix 17.1) until the Month 3 visit (Visit 5) or study withdrawal. For Cohort 5, the subjects may return to the clinic earlier after the first month, depending on the duration of the therapy (at least 6 to 12 weeks) and imaging at 6 weeks for thrombus resolution.

During study drug interruptions and after study drug discontinuation, subjects will be followed for efficacy and safety endpoints and SAEs until the Month 3 visit (Visit 5) or earlier in Cohort 5 subjects (6-12 weeks). A 30 day Follow-Up Visit (Visit 9) for safety assessment is required after the Month 3 visit (for Cohort 5, the intended duration of treatment is 6 to 12 weeks).

At these monthly on-site visits, anti-FXa levels assessments and aPTT measurements will be performed for the subjects on SOC with LMWH or SP Xa inhibitor, fondaparinux levels if applicable, and INR assessments will be performed for the subject on SOC with VKA. Additional interim visits may be scheduled, at the Investigator's discretion, for anti-FXa levels/INR monitoring.

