6.3.3.2. Month 2 (Visit 4) Procedures

- Record concomitant medications
- Count unused study drug tablets/ bottles/syringe and calculate compliance
- Dispense study drug medication and review dosing instructions
- Perform physical examination (see Section 9.10)
- Record vital signs (Section 9.9)
- Safety review for AEs/SAEs

- Review for endpoint events (VTE, bleeding)
 - The follow-up imaging performed if needed, must be always performed with the same modality as the initial diagnostic study

6.3.4. End of Main Treatment Period Visit (Month 3 or at least 6-12 weeks for Cohort 5, Visit 5) Procedures

All randomized subjects including those that have discontinued treatment will have an EOT assessment at Month 3 (within a ± 5 -day window).

The following will be performed at this visit:

- Perform physical examination (see Section [9.10](#))
- Vital signs (Section [9.9](#))
- Review concomitant medications
- Count unused study drug tablets/ bottles/syringe and calculate compliance
- Safety review for AEs/SAEs
- Review for endpoint events (VTE, bleeding)
 - Radiologic examination using the same diagnostic technique used at baseline to determine the thrombotic burden (see Section [7.1](#)).
 - VTE Radiologic Imaging (see Section [7.1](#)).
- Take samples for the following:
 - Liver function tests [ALT, AST, TBL, and ALP]
 - Serum creatinine
 - Hematology
 - Urine pregnancy test
- Dispense study drug medication and review dosing instructions per subject/parent's request and at the Investigator's decision to extend study treatment. After Month 3, the distribution of edoxaban or SOC may be for a 3-month period to align with the visit schedule, with the Sponsor's approval.

6.4. Extension Period (beyond Month 3 - Month 6, 9 and 12; Visits 6, 7, 8)

Per subject/parent's request and at the Investigator's decision, study treatment can be extended up to 12 months. At any time during the extended period, a subject can discontinue treatment and the study. In such a case a discontinuation study visit will be performed with a subsequent 30-day safety Follow-Up Visit (see [Table 17.1](#)).

The subjects on extended treatment will be followed for safety and efficacy assessment including bleeding events, recurrent VTE, and any treatment-related AEs at visit for Months 6 (Visit 6), 9 (Visit 7), and 12/ Discontinuation (Visit 8). Additionally, the subject will have a Follow-Up Visit (Visit 9) for safety assessment 30 days after treatment cessation. At Month

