	
• Spiral CT pulmonary angiography (CTPA)• Magnetic resonance pulmonary angiography (MRPA) 
Alternative imaging techniques:
 
• Cardiac angiography• Conventional pulmonary angiography• echocardiography
Sinovenous thrombosis	
• Brain MRI, including T2 imaging and MRI with venography (MRV)• Pre and post-contrast CT scan with venography (CTV) 
Alternative imaging techniques:
 
• Doppler flow US; if fontanelle open
Renal Vein thrombosis	
• US
Splanchnic and hepatic veins and vena cava	
• Doppler/US• CT/Scan

In certain cases, the use of 2 techniques may be required to objectively confirm the diagnosis of recurrent VTE. Further recommendations will be provided in the imaging manual but will be left for Investigator's discretion.

Diagnosis of fatal VTE is based on 1 or more of the following:

- Objective diagnostic testing
- Autopsy
- Death which cannot be attributed to a documented cause and for which VTE cannot be ruled out.

Thrombotic burden will be assessed by comparison of the diagnostic method used at baseline and at Month 3 \pm 5 days (for Cohort 5, at 6 to 12 weeks \pm 5 days) in the absence of symptomatic recurrent VTE. Hence, the same imaging technique that is used at the enrollment of the subject into the study will be required to be used at the end of the observational period \pm 3 days. A thrombotic burden endpoint will be registered if there is no regression of the thrombus size or extension of the thrombus at Month 3 visit \pm 3 days (for Cohort 5, at 6 to 12 weeks \pm 3 days) after randomization.

Additionally, thrombotic burden will be assessed at Month 12 \pm 5 days / Discontinuation Visit, for those subjects who participate in the Extension Period.

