7.5. Appropriateness of Selected Efficacy Endpoint(s)

Definitions of outcomes in U312 are based on presentations/discussions at the Perinatal and Paediatric Haemostasis Subcommittee meetings during the 56th–58th Scientific and Standardization Committee (SSC) Meetings of the International Society on Thrombosis and Haemostasis (ISTH)²¹.

The proposed primary efficacy endpoint in the Phase 3 VTE study (U312) is a composite endpoint consisting of the incidence of symptomatic recurrent venous thromboembolic disease, death as a result of VTE, or no change or extension of thrombotic burden within the 3-month +3 days study period.

In children with VTE disease, the incidence of “no change in thrombotic burden” has been reported in several clinical pediatric studies as 14.8%¹⁶, 17% and 18%¹⁷. Lack of thrombus resolution has been reported as a prognostic factor for the development of post-thrombotic syndrome (PTS)¹⁸. PTS is a known complication of VTE that children must endure as chronic sequelae that adversely impacts quality of life (QOL) for many decades. Goldenberg et al. conducted a systematic review of PTS in children in 2010. A total of 997 subjects were assessed

for PTS. In this review, the frequency of PTS post DVT (Upper Extremity/Lower Extremity) was reported as high as 26%. In Goldenberg's review, the lack of thrombus resolution was mentioned as a prognostic factor for the development of PTS.

The clinical significance of "no change in thrombotic burden" in the incidence of PTS is therefore clearly documented. In order to ensure adequate adjudication of this endpoint, the Sponsor will be implementing several steps:

1. The same imaging technique that is used at the enrollment of the subject into the study will be required to be used at the end of the observational period
2. Detailed instructions ensuring consistency in obtaining images for each of the techniques will be provided to the study sites
3. Both initial and follow-up imaging will be independently and blindly assessed by an appropriately qualified central adjudication committee.

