11.2. General Statistical Considerations

All efficacy analyses will be based on the mITT Analysis Set or PP Analysis Set and will be performed based on the treatment arm assigned at randomization. All statistical tests will be two-sided at a 5% significance level, unless otherwise specified.

Safety analysis will be performed using the Safety Analysis Set. Subjects will be analyzed according to actual treatment received.

Unless otherwise specified, the baseline value of an efficacy variable for a subject is the last non-missing measurement before the first administration of study drug, and the baseline value of a safety variable is the last non-missing measurement before the first dose of the study drug.

In general, missing data will not be imputed for the purpose of data analysis. No visit windows will be used for analysis.

Continuous variables will be summarized by the number of observations, mean, standard deviation, median, and minimum and maximum values. Categorical variables will be summarized using frequency counts and percentages. Summary statistics will be presented by treatment arm.

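### The Month 3 scan may be taken later than the primary-analysis cut-off, so a failing scan that is on time by the visit schedule can be censored as event-free

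*Combined protocol and SAP*

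**What the plan says.** The current text gives several limits for the same scan.

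- **Section 6.3.4:** "All randomized subjects including those that have discontinued treatment will have an EOT assessment at Month 3", within ±5 days. The radiologic examination is part of that visit.
- **Table 17.1:** the window for Visit 5 (Month 3) is ±5 days.
- **Section 7.1, first thrombotic-burden sentence:** "Thrombotic burden will be assessed by comparison of the diagnostic method used at baseline and at Month 3", followed by ±5 days.
- **Section 7.1, next two sentences:** the follow-up imaging is required within ±3 days, and "A thrombotic burden endpoint will be registered if there is no regression of the thrombus size or extension of the thrombus at Month 3", followed by ±3 days.
- **Section 7.5:** the composite is defined with "no change or extension of thrombotic burden within the 3-month +3 days study period".
- **Section 11.4.1.1:** the censoring rule reads "did not have a primary efficacy outcome during the 3 months + 3 days period will be censored at 3 months + 3 days", with an earlier last complete assessment for outcomes taking precedence.
- **Synopsis, Primary Efficacy Analyses:** "primary efficacy events occurring from randomization through the end of the 3-month treatment period". It adds 3 days only for Cohort 5.
- **Section 3.3:** events toward the 68 are counted from randomization up to the final Month 3 visit, within the first 3-month treatment period.
- **Section 11.2:** "No visit windows will be used for analysis".
- **Section 6.3.3:** "subjects will return to the clinic every 30 days" (±5), which puts Month 3 at about day 90.

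Section 7.1 gives Cohort 5 the same pair of windows, ±5 and ±3 days around 6 to 12 weeks.

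**The concern.** No change or extension of thrombotic burden is one of the three components of the primary composite. Absent a symptomatic recurrence, it is normally read from this one scheduled scan. Section 11.4.1.1 counts days from randomization, and no rule in the documents assigns a later scan back to Month 3. A subject whose failing scan falls after the cut-off, but within ±5 days, is therefore analysed as event-free.

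Three things are at stake:

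- **An undefined event set.** Two statisticians following the text could analyse different primary events.
- **Two different counts.** The same scan can count toward the number that stops randomization and be absent from the analysis. The analysed count can then fall below the 68 on which the 80% power rests.
- **Discretion.** The trial is open-label, so the window should not be left to be chosen after data have been seen.

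**Working it through.** **1. The plan's own figure.** Section 11.6 gives a margin of 1.5, an assumed hazard ratio of 0.76, two-sided alpha of 0.05 and 68 events. With 1:1 allocation,

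Power = Φ( ln(1.5/0.76) × √d / 2 − 1.96 )

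At d = 68: 0.680 × 8.246 / 2 − 1.96 = 0.843, so power is 0.800. The stated 80% reproduces.

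**2. How wide is the gap?** It depends on what 3 months means.

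- *Same anchor* (Month 3 and 3 months are the same day): the visit window ends at +5 and the analysis at +3. Days +4 and +5 are exposed, a gap of 2 days.
- *Month 3 at day 90, 3 months by calendar:* the last on-schedule scan is day 90 + 5 = 95. Three calendar months last 89 to 92 days, so the cut-off is day 92 to 95. The table runs over every start date in a four-year cycle.

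| 3 calendar months (days) | Cut-off (day) | Gap (days) | Share of start dates |
|---|---|---|---|
| 92 | 95 | 0 | 57.8% |
| 91 | 94 | 1 | 21.4% |
| 90 | 93 | 2 | 14.8% |
| 89 | 92 | 3 | 6.0% |

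The mean gap is 0.214 × 1 + 0.148 × 2 + 0.060 × 3 = 0.69 day.

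**3. Share of events found by scan (assumption).** Section 7.5 cites rates of no change in burden of 14.8% to 18%. Section 11.6 plans a 28% control event rate. The share is then 14.8/28 = 0.529 to 18/28 = 0.643. This is rough, because Section 1.1 shows that the cited rates come from follow-up of up to several years.

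**4. Events lost and power.** Events lost = 68 × share × late fraction. This assumes that late scans count toward the 68 but not in the analysis. The late fractions are assumptions; the documents give no scan timing.

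| Late fraction of failing scans | Events lost | Events analysed | Power |
|---|---|---|---|
| 0 (cut-off covers the window) | 0 | 68 | 80% |
| 5% | 1.8–2.2 | 66.2–65.8 | 79% |
| 0.69/11 = 6.3% (calendar reading, even timing) | 2.2–2.7 | 65.8–65.3 | 78–79% |
| 2/11 = 18% (same anchor, even timing over 11 days) | 6.5–7.9 | 61.5–60.1 | 76–75% |
| 30% | 10.8–13.1 | 57.2–54.9 | 73–71% |

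**5. Check on the formula.** A simulation used 137 per arm, 28% control risk, a hazard ratio of 0.76, a Cox model with treatment only and 600 runs per setting, at scan shares of 0.53 and 0.64. Power was 0.80/0.79 with 5% late, 0.76/0.73 with 2/11 late and 0.74/0.72 with 30% late. Counting every scan in the ±5-day window gave 68.7 events and power 0.80. The simulation fixes the sample size, so it checks the loss formula and not the stopping rule.

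**6. If the stopping count also leaves out late scans.** Randomization then continues until 68 countable events accrue, so the cost is subjects, not power. With 2/11 late, 274 × 68/61.5 = 303 to 274 × 68/60.1 = 310 subjects would be needed.

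**The case against.** The best defence is that the endpoint-defining text largely agrees. Section 7.1 registers the burden endpoint at ±3 days, and Sections 7.5 and 11.4.1.1 stop at + 3 days. On that reading ±5 is only visit tolerance, and a day +5 scan is a permitted visit that misses the endpoint window. This is a fair reading, but it leaves Section 6.3.4, Table 17.1 and Section 7.1's own first burden sentence giving sites a window in which a failure will not count.

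Other points carry some weight:

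- The statement in Section 11.2 may mean analysis by nominal visit, which would keep a late scan at Month 3. That does not settle the matter, because Section 11.4.1.1 counts time from randomization.
- On the calendar reading the gap is zero for most start dates. For the rest, whether a scan on the last allowed days counts would depend on the date of randomization.
- Section 3.3 also confines events to the first 3-month treatment period. If both counts used the Section 11.4.1.1 cut-off, power would be kept.
- Section 11.7 leaves definitions to an SAP finalised before database lock. No such rule appears in the documents, and in an open-label trial that timing is weak protection.
- The cut-off applies to both arms and adjudication is blinded, so no direction of bias is shown. The secondary composite, to last dose + 30 days, would still count the scan in subjects treated to Month 3, but it does not decide non-inferiority.

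These points limit the likely size. None removes the contradiction.

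**Conclusion.** The concern holds. The primary-analysis rule, as written, can drop a failure found on a scan that kept to the visit schedule, and the documents give different cut-offs for the same endpoint. This is an error in a stated rule for the confirmatory test and needs correcting even if the loss proves small.

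Confidence is high in the inconsistency and low in its size. The effect runs from none to about 2 or 3 events on the calendar reading with even timing (power 78–79%), and to about 6.5 to 8 events on the same-anchor reading with even timing (75–76%). The 30% case is only an outer bound. All these figures rest on the assumed scan share and scan timing. Power falls only if late scans count toward the 68 but not in the analysis.

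**What to change.** - Define Month 3 as a number of days from randomization.
- Use one window for the scheduled scan in Sections 6.3.4, 7.1 (including its Cohort 5 wording), 7.5 and 11.4.1.1, the synopsis and Table 17.1. Either width can be made consistent; ±5 days leaves the visit schedule as it is.
- In the primary analysis, count any adjudicated burden finding on the scheduled Month 3 scan taken within that window, and set the cut-off at or after the window's end.
- State how a scan outside the window is handled.
- Count the 68 events in Section 3.3 by the same rule.

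**Cost.** No extra subjects, visits or scans. The change is to wording, but it touches the primary endpoint window, so it needs a protocol amendment under Section 15.7 and a matching SAP. Keeping ±5 days may lengthen the primary window by about two days and set it slightly apart from the + 3 day bleeding window in Section 11.4.3.1. Choosing ±3 days gives sites less room to book the scan.
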